2.3 Exploratory Objectives & Endpoints

Exploratory objectives will include the following:

- 2.3.1 Describe pharmacodynamics (PD) effects of alisertib in peripheral blood and/or bone marrow samples.

Serial blood and/or bone marrow samples will be collected at specific timepoints. Flow cytometry, colony forming assays, AURKA autophosphorylation assays, and in vitro cultures of patient specimens to assess the effect of MLN8237 on megakaryocytes and other hematopoietic cells will be measured.

- 2.3.2 Evaluate the relationship between biomarker expression levels and response to alisertib.

Changes in biomarker expression levels from baseline will be measured (using PD samples) to correlate with response to alisertib therapy. Biomarkers will include a) genes encoding key enzymes in Aurora kinase signaling, b) markers of cellular aneuploidy and apoptosis, and c) markers of megakaryocytic differentiation.

- 2.3.3 Evaluate reduction in splenomegaly by palpation (MF arm only).

Patients will be examined for splenomegaly by palpation once per cycle and change from baseline will be calculated over time.

- 2.3.4 Evaluate improvement in MF symptoms (MF arm only), as assessed by the Myeloproliferative Neoplasm Symptom Assessment form (MPN-SAF).

The MPN-SAF will be administered to patients in the MF arm only once per cycle. Changes in symptom scores over time will be calculated.

- 2.3.5 Assess change in bone marrow fibrosis in patients in the MF arm. Bone marrow will be assessed at screening and after cycle 6 in this population.

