5.0 STUDY PROCEDURES

5.1 Schedule of Events for MF Patients

	Baseline	On-Treatment ⁱ							Off-Treatment	
	Screening	Cycle 1 ^a				Cycles 2-6 ^q +/- 2 days		Cycle 7+ ^m +/- 2 days	EOT Visit ^o	EOS Visit ^p
		D1 ⁱ	D4 (+/- 1d)	D8 (+/-2 d)	D15 (+/-2 d)	D1 ⁱ	D15	D1		
Informed consent ^v	X									
Medical history ^r	X									
Physical exam ^b	X	X		X	X	X		X	X	X
ECOG status ^s	X	X		X	X	X		X	X	X
Vital signs ^c	X	X		X	X	X		X	X	X
12-lead ECG ^d	X									
Hematology ^{e,t}	X	X	X	X	X	X	X	X	X	X
Chemistry ^{f,t}	X	X	X	X	X	X	X	X	X	X
DIC screen ^{g,t}	X									
PT(INR)/aPTT ^g		X	X	X	X	X				
Pregnancy test ^{h,t}	X	X								
Palpation for splenomegaly ^l	X	X				X		X		
MPN-SAF ^l	X	X				X		X		
Bone marrow biopsy & aspirate ^k	X							X ^k	X	
Bone marrow collection for PD studies ^{i,j}					X					
Blood collection for PD studies ^{i,j}		X			X	X	X			
Treatment ⁿ					X					
Adverse events ^u	X	X		X	X	X		X	X	X
Concomitant meds	X	X		X	X	X		X	X	

^a One cycle = 21 days.

^b Includes height (baseline only) and weight. Baseline physical exam within 14 days of registration.

^c Vital signs include diastolic and systolic blood pressure, heart rate, and oral temperature; C1D1 vital signs should be taken pre-dose(+/-30 mins) as well as about 2 hours(+/-30mins) post dose.

^d A 12-lead ECG will be performed at baseline and thereafter only as clinically indicated. Baseline ECG within 14 days of registration

- ^e Hematology panel to include hematocrit, hemoglobin, white blood cell count with differential, and platelet count. Samples should be collected days 1, 4, 8, and 15 of cycle 1, days 1 and 15 of cycles 2-6, and then day 1 of all cycles thereafter (a window of +/- 2 days is permitted for all timepoints). See footnote t.
- ^f Chemistry panel to include the following: BUN, creatinine, sodium, potassium, chloride, bicarbonate, glucose, uric acid, LDH, total bilirubin, direct bilirubin, ALP, AST (SGOT), ALT (SGPT), albumin, magnesium, phosphate, and calcium. Samples should be collected days 1, 4, 8, and 15 of cycle 1, days 1 and 15 of cycles 2-6, and then day 1 of all cycles thereafter (a window of +/- 2 days is permitted for all timepoints). See footnote t. Beyond Cycle 6, magnesium and phosphate testing is not required (as part of the chemistry panel).

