- ^m Beyond Cycle 6, if the patient's condition is stable, then they will be required to come in only on Day 1 of every even cycle (every 6 weeks) for study visit. In that case, for those visits when patient is not coming to clinic for study visit, CBC and CMP only will be done in an outside laboratory convenient for the patient, and results will have to be faxed to the clinic. Patients can start their treatment at home only after the treating physician has reviewed the laboratory results and determined that they are able to continue treatment. For these cycles, the study coordinator will contact the patient on/prior to Day 1 to inform them if they can or cannot start the new cycle, and also check compliance regarding study drug intake.
- ⁿ Patients will be administered orally on days 1-7 of each cycle (1 cycle = 21 days); patients may remain on treatment until development of unacceptable toxicity or progression of disease.
- ^o Patients will have an end of treatment (EOT) visit approximately 30 days (+10 days) after the last dose of treatment; if a bone marrow was carried out at disease progression, this will be considered the EOT marrow and does not need to be repeated at the EOT visit.
- ^p Patients will have a final end of study (EOS) visit approximately 6 months (+/- 30 days) after the last dose of treatment to assess for late-onset toxicity.

^q Labs required only on days 1 and 15 of cycles 2-6, but in the event of cycle 1 toxicity or at treating investigator's discretion, additional interim labs may be performed per standard of care.

^r Baseline Medical History within 14 days of registration

^s Baseline ECOG Status within 14 days of registration.

^t Baseline Hematology, Chemistry, DIC screen, Pregnancy Test, within 14 days of registration

^u Baseline Adverse Events and Concomitant Medications within 14 days of registration.

^v Informed consent should be obtained within 28 days of registration.

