6.0 ENDPOINT ASSESSMENT

6.1 Primary Endpoint

The primary objective of this pilot study is to determine the safety profile of alisertib in patients with AMKL and in patients with MF.

Adverse events will be defined according to the National Cancer Institute's Common Terminology Criteria for Adverse Events (NCI CTCAE) version 4.0. The number, frequency, and severity of adverse events will be recorded every cycle for each population. All patients who receive at least 1 dose of alisertib will be considered evaluable for this endpoint.

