7.1 Adverse Event Monitoring

Adverse event data collection and reporting, which are required as part of every clinical trial, are done to ensure the safety of subjects enrolled in the studies as well as those who will enroll in future studies using similar agents. Adverse events are reported in a routine manner at scheduled times during a trial (see Section 5 for timepoints). In addition, certain adverse events must be reported in an expedited manner to allow for optimal monitoring and patient safety and care.

All patients experiencing an adverse event, regardless of its relationship to study drug, will be followed until:

- the adverse event resolves or the symptoms or signs that constitute the adverse event return to baseline;
- any abnormal laboratory values have returned to baseline;
- there is a satisfactory explanation other than the study drug for the changes observed; or
- death.

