10.0 STATISTICAL CONSIDERATIONS

10.1 Statistical Analysis

10.1.1 Primary Endpoint

The primary objective of this pilot study is to determine the safety profile. All adverse events (AEs) will be summarized using frequencies and percentages. These percentages will be subclassified by type of AE, timing of AE in the treatment cycle, frequency and attribution of AEs (treatment related or not).

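### After cycle 6, stable MF patients have no scheduled adverse-event enquiry in alternate cycles, although the primary endpoint calls for recording in every cycle

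*Combined protocol and SAP*

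**What the plan says.** Section 6.1 states: "The primary objective of this pilot study is to determine the safety profile of alisertib in patients with AMKL and in patients with MF". Sections 2.1 and 6.1 both add: "The number, frequency, and severity of adverse events will be recorded every cycle for each population". Section 10.1.1 breaks the adverse-event percentages down by, among other things, "timing of AE in the treatment cycle". For when events are collected, Section 7.1 points to the schedule: "Adverse events are reported in a routine manner at scheduled times during a trial (see Section 5 for timepoints". Section 11.4 makes data due at the end of each cycle once cycle 1 is over.

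The Section 5.1 table marks adverse events on Day 1 of Cycle 7+, but footnote m governs that column. For stable MF patients beyond cycle 6 it says "they will be required to come in only on Day 1 of every even cycle (every 6 weeks) for study visit". In the remaining cycles it provides for:

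- a CBC and CMP at an outside laboratory;
- review of those results by the treating physician before the patient starts at home;
- a coordinator contact: "For these cycles, the study coordinator will contact the patient on/prior to Day 1 to inform them if they can or cannot start" the cycle, and to check drug compliance.

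Section 4.2 describes the same arrangement, except that it puts the visits in odd cycles. Neither place mentions adverse events or concomitant medications for the cycles without a visit.

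**The concern.** Footnote m removes the visit at which adverse events would have been asked about. It puts in its place a contact whose listed purposes do not include them. A site that follows the schedule to the letter would not meet the per-cycle recording rule for the primary endpoint.

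The events most exposed are those that a blood count or chemistry panel cannot show. Section 8.1.10 lists several as common: nausea, diarrhea, stomatitis, fatigue, somnolence, confusion, dizziness, rash. Section 1.5 links the central nervous system effects to peak plasma concentration, so some may be brief and hard to date or grade weeks later. Section 1.6 says that alisertib has not been studied in MF and that safety needs careful review. All 24 subjects may be MF patients (Section 10.2).

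The two populations are also treated differently. AMKL patients keep Day 1 laboratory tests and examination in every cycle from cycle 7 on (Section 5.2, footnote l), so ascertainment would differ between groups whose safety is recorded separately.

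**Working it through.** **Inputs.** Cycle length: "One cycle = 21 days" (Section 5.1, footnote a). Dosing on days 1-7 (Section 4.2). Visit every second cycle after cycle 6, stated as every 6 weeks (footnote m and Section 4.2). All figures below are nominal days, without visit windows or treatment delays.

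**The plan's own interval.** 2 cycles × 21 days = 42 days; 42 / 7 = 6 weeks. This agrees with the stated figure.

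**Which cycles lack a scheduled enquiry, cycles 7 to 12.**

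| Rule | Visits on Day 1 of | No scheduled enquiry in | Gaps between assessments, from C6D1 |
|---|---|---|---|
| Even (footnote m) | 8, 10, 12 | 7, 9, 11 | 42, 42, 42 days |
| Odd (Section 4.2) | 7, 9, 11 | 8, 10, 12 | 21, 42, 42 days |

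Under either rule 3 of 6 cycles have none. The rules differ only in which cycles are missed and in the first gap.

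**Recall time.** Count from Day 1 of the first cycle in a 42-day gap. The next visit falls on day 1 + 42 = 43, so an event on day d is asked about 43 − d days later. For d = 1 to 7 that is 42 down to 36 days. With an enquiry every cycle the next one falls on day 22, and the delay is 22 − d, or 21 down to 15 days. Each 42-day gap holds two dosing weeks, so the patient must recall not only the event but also which dosing week it followed. The breakdown by timing within the cycle depends on that.

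**Does another provision supply the enquiry?**

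- The new-cycle criteria in Section 4.2, including resolution of related toxicity, are introduced for cycles 1-6 only.
- The diary in Section 4.2 covers compliance and missed doses with reasons. It is not described as a symptom record.
- Footnote m bases permission to start at home on review of laboratory results.
- Counselling on sedation in Section 4.4.3 is attached to visits and adverse-event assessments, and neither is scheduled in these cycles.

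**With the query added to the contact.** Every cycle has an enquiry and the nominal interval returns to 21 days.

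**The case against.** The strongest reply is that the plan is silent here and forbids nothing. The duty to record events every cycle is general, footnote m does not waive it, and the adverse-event row stays marked for Cycle 7+. A sensible coordinator would ask, and events from a skipped cycle can be entered with onset dates at the next visit. Fewer visits were a deliberate choice in Amendment 8, made for patient convenience. Much of this stands, and it rules out several stronger readings that a reader might infer.

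- **That footnote m excludes adverse-event enquiry.** Its word *only* attaches to the outside laboratory tests, and Section 4.2 omits the word. It limits what is drawn, not what may be asked.
- **That nothing about safety is learned in these cycles.** Cytopenias and chemistry abnormalities remain visible, serious events must be reported on discovery or occurrence (Section 7.2.3), and toxicity that interrupts dosing can surface through the diary and compliance check.
- **That half of all late cycles in the trial are affected.** The gap concerns MF patients judged stable and still treated after cycle 6. AMKL patients and unstable MF patients keep a visit each cycle.
- **That late-cycle adverse-event rates are biased downward.** Under-recording is plausible, but nothing in the documents shows it or gives it a size, and Section 10.1.1 plans no comparison of early with late cycles.

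The reply does not remove the gap. Section 7.1 sends the reader to Section 5 for collection times, and Section 5 schedules none in these cycles. Whether events are asked about then depends on the habits of each site.

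**Conclusion.** The point holds as a mismatch between the primary-endpoint rule and the schedule. For stable MF patients after cycle 6, the scheduled adverse-event interval is 42 days where the endpoint definition implies 21, and half of the cycles (3 of 6 in cycles 7 to 12) have no scheduled enquiry. The consequence is confined to non-serious, non-laboratory events that do not interrupt dosing: they may be missed, or dated to the wrong cycle in the Section 10.1.1 breakdown.

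This rests on reading the listed activities as the schedule that sites will follow, and on nominal cycle lengths. The documents do not say how many patients would reach cycle 7 or be judged stable, so the number of affected patients and the amount of any under-recording are unknown. The point deserves correction because the remedy is cheap and the endpoint is primary. It does not undermine the safety analysis as a whole.

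Two related matters are secondary. The odd-cycle and even-cycle wordings contradict each other, and the even rule has no routine visit at C7D1, where footnote k requires a marrow; these places must be reconciled. The symptom form is affected too, since Section 2.3.4 says "The MPN-SAF will be administered to patients in the MF arm only once per cycle", but that endpoint is exploratory.

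**What to change.** In Section 4.2 and in footnote m of Section 5.1, add to the coordinator contact in each cycle without a visit a scripted question about adverse events and concomitant medications since the last assessment. Record onset date and grade for each event on that cycle's eCRF. In the same edit, reconcile the odd-cycle and even-cycle wordings and check the result against the C7D1 marrow in footnote k.

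The cost is a few minutes on a contact that is already made, and one extra form per skipped visit. The reduced visit schedule, and the convenience it was meant to give, stay as they are.

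If the sponsor prefers not to add the query, Sections 2.1 and 6.1 should state the actual interval for these patients. That makes the text consistent but leaves the longer recall in place.

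Collecting the MPN-SAF by mail or phone at the same contact is optional. Patients score the form themselves (Appendix II, footnote 10), so phone completion would change how it is administered.

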4.2 Treatment Administration

Alisertib will be administered orally BID on days 1-7 of each cycle; one cycle is defined as 21 days (days 8-21 will be rest days). Patients will be instructed to take each oral dose of alisertib with 8 ounces (1 cup, 240 mL) of water, with or without food. Doses on the same day should be taken approximately 12 hours apart (but *at least* 6 hours apart). All tablets are to be ingested whole; patients who have difficulty swallowing tablets will be excluded from the study. Antiemetic agents may be administered at the discretion of the investigator. Neutralizing antacids and calcium-containing supplements cannot be taken from 2 hours prior to alisertib dosing until up to 2 hours after dosing.

Patients will be dispensed the appropriate number of tablets required for each cycle. Treatment compliance will be assessed based on return of unused alisertib tablets and completion of a study medication diary; patients will be asked to bring completed diaries and pill bottles to each visit, and compliance will be reviewed by the study team each cycle. For MF patients only, from Cycle 1-6, on Day 1 of each cycle, when the patient comes in for clinic visit, they will be given study drug supply for one cycle (1 cycle=21 days). Beyond Cycle 6, if the patient's condition is stable, then they will be required to come in on Day 1 of every odd cycle (every 6 weeks) for study visit. In that case, patients will be given study drug supply for 2 cycles.

If a dose is missed due to patient error/oversight, they will be instructed to take the dose within 6 hours of the normal time. If more than 6 hours have elapsed, that missed dose should be omitted, and the patient should resume treatment at the next scheduled dosing time point. All missed/omitted doses and the reason will be reported on the diary. If a dose is vomited, it should not be re-taken. If a dose is held due to toxicity or investigator's discretion, the patient should be instructed to resume treatment at the investigator's discretion, taking into account all of the dose modification/discontinuation guidelines provided below.

From Cycle 1-6, in order for each new cycle of therapy to begin, MF patients must meet the following criteria: (if the cytopenias in AMKL patients are considered-disease related/due to AMKL then the following neutrophil and platelet count requirements do not apply. If cytopenias are considered due to the study drug, then the counts must be

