- ANC must be $\geq 1000/\text{mm}^3$
- Platelet count must be $\geq 50,000/\text{mm}^3$
- In addition, all toxicities considered to be related to therapy with alisertib must have resolved to \leq Grade 1 or the patient's baseline values

For MF patients only, from Cycle 1-6 patients will be required to come in for study visit at beginning of every cycle (every 3 weeks). Beyond Cycle 6, if the patient's condition is stable, then they will be required to come in on Day 1 of every odd cycle (every 6 weeks) for study visit. In that case, for those visits when an MF patient is not coming to clinic for study visit, CBC and CMP will be done in an outside laboratory convenient for the patient, and results will have to be faxed to the clinic.

Patients can start their treatment at home only after the treating physician has reviewed the laboratory results and determined that they are able to continue treatment. For these cycles, the study coordinator will contact the patient on/prior to Day 1 to inform them if they can or cannot start the new cycle, and also check compliance regarding study drug intake.

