11.4 Data Submission and Monitoring/Auditing

Once a subject is confirmed and registered to the study, eCRFs should be submitted through NOTIS according to the detailed data submission guidelines (will be provided in a

separate document). Generally, all data during the first cycle must be submitted on a weekly basis. Thereafter data will be due at the end of each cycle.

This study will be conducted in compliance with the Data Safety Monitoring Plan (DSMP) of the Robert H. Lurie Comprehensive Cancer Center of Northwestern University (please refer to Appendices for additional information). The level of risk attributed to this study requires high intensity monitoring, as outlined in the DSMP. The assigned QAM, with oversight from the Data Monitoring Committee, will monitor this study in accordance with the study phase and risk level.

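### Stable MF patients after cycle 6: adverse events are to be recorded every cycle, but no adverse event enquiry is specified before the home-started cycle, so the first scheduled enquiry can come 36 to 42 days after an event

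*Combined protocol and SAP*

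**What the plan says.** Safety is the primary objective. Section 6.1, like Section 2.1, states: "The number, frequency, and severity of adverse events will be recorded every cycle for each population". Section 7.1 makes Section 5 the timetable: "Adverse events are reported in a routine manner at scheduled times during a trial (see Section 5 for timepoints". Section 4.3 does the same for toxicity assessment. On data submission after the first cycle, Section 11.4 says: "Thereafter data will be due at the end of each cycle". The primary analysis in Section 10.1.1 is descriptive: "These percentages will be subclassified by type of AE, timing of AE in the treatment cycle".

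In the MF schedule (Section 5.1) the AE row is marked at Day 1 of cycle 7 onward, and that column carries footnote m. Under footnote m and Section 4.2, a stable MF patient then attends every 6 weeks. Section 4.2 says odd cycles and footnote m says even cycles; the spacing is the same. Drug is dispensed to match: "In that case, patients will be given study drug supply for 2 cycles".

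Three things are named for the cycle without a visit:
- Blood tests: "CBC and CMP only will be done in an outside laboratory convenient for the patient".
- A physician release. The patient may start at home "only after the treating physician has reviewed the laboratory results and determined that they are able to continue treatment".
- A coordinator contact, in which "the study coordinator will contact the patient on/prior to Day 1 to inform them if they can or cannot start the new cycle" and checks drug intake.

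**The concern.** Neither Section 4.2 nor footnote m says that anyone asks about AEs before the home-started cycle. Blood counts and chemistry do not show sedation, confusion, fatigue or stomatitis, all of which are listed risks in Section 1.5.2. The sedation counselling in Section 4.4.3 is attached to study visits and AE assessments after cycle 1 begins, so it is not scheduled for this cycle either.

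Two things are at stake. The first is dosing. Section 4.3.2 has no cycle limit: a qualifying related non-hematological toxicity still calls for a dose reduction and for recovery before treatment resumes. The Section 4.2 rule that related toxicity must have recovered before a new cycle starts is, however, worded for cycles 1 to 6. After that, a patient holding two cycles of drug can begin the second course with no scheduled question that would bring a symptomatic toxicity to the physician's attention.

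The second is the endpoint. The breakdown by timing within the cycle needs onset dates. For these patients the dates of symptomatic events may have to be recalled across two dosing courses, for a drug whose listed effects include memory loss.

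**Working it through.** **Inputs.** Cycle length is 21 days, with dosing on days 1 to 7 (Sections 4.1 and 4.2). Stable MF patients after cycle 6 attend on Day 1 of every second cycle (Section 4.2 and footnote m). The visit window from cycle 7 is plus or minus 2 days (Section 5.1).

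**The plan's own figure.** 2 × 21 = 42 days = 6 weeks, which agrees with the stated visit interval.

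**Cycles with a scheduled AE assessment.** Take cycles 7 to 18 as an illustrative span of 12 cycles. Even wording: visits at cycles 8, 10, 12, 14, 16 and 18. Odd wording: cycles 7, 9, 11, 13, 15 and 17. Either way, 6 of 12 cycles have a scheduled AE assessment.

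**Lag from event to first scheduled enquiry.** Let a non-serious, non-laboratory event begin on dosing day d, with d = 1 to 7, and use nominal days.

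| Situation | Next scheduled enquiry | Lag formula | Range (days) | Mean (days) |
|---|---|---|---|---|
| Clinic-started cycle, current plan | day 43 | 43 − d | 36 to 42 | 273/7 = 39 |
| Home-started cycle, current plan | its day 22 | 22 − d | 15 to 21 | 126/7 = 18 |
| Either cycle, enquiry added to the contact | day 22 at the latest | at most 22 − d | 15 to 21 | 126/7 = 18 |

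With the 2-day window the first row widens to 34 to 44 days. Averaged over the two cycles, the current plan gives (39 + 18)/2 = 28.5 days, against 18 with the enquiry added. The long lag applies to 7 of every 14 on-drug days in this group.

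**Dosing between enquiries.** Counting from a clinic Day 1, dosing falls on days 1 to 7 and days 22 to 28, and the next scheduled enquiry is on day 43. Two courses are taken per enquiry. An enquiry before day 22 makes it one course per enquiry and raises enquiries per two cycles from 1 to 2 (12 of 12 in the illustrative span).

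**The case against.** The best defence is that nothing forbids the recording. Footnote m moves the visit and limits the laboratory tests. The AE mark stays at Day 1 of cycle 7 onward, Sections 2.1 and 6.1 still require recording every cycle, and Section 11.4 still makes data due each cycle. A site could satisfy all of these by asking during the contact that already exists. Recording every cycle could also mean attributing each event to its cycle, which a 6-weekly visit can do. That stands to this extent: the enquiry is unspecified, not prohibited. A site that follows the stated steps exactly will nevertheless not make it.

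There are also partial safeguards:
- The medication diary records missed doses with reasons, and compliance is reviewed each cycle (Section 4.2). This fixes the dosing calendar. It is not described as a record of symptoms or their onset.
- The physician must determine that treatment can continue, and that judgement may include toxicity. The only input named for it is the laboratory results.
- By cycle 7 patients and caregivers have been counselled repeatedly about sedation.
- Laboratory abnormalities are seen every cycle, and serious events are reported on discovery (Section 7.2.3).

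The reduced visits are a deliberate convenience for stable long-term patients, and an event collected late still counts in a descriptive table. Both points are fair, and they limit the consequence.

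Three stronger readings are tempting but unsupported. One is that AEs are lost: they can be collected at the next visit. Another is that toxicity rules lapse after cycle 6: Section 4.3.2 continues to apply. The third is that the blank AE cell at Day 15 of cycles 2 to 6 is the same defect: Day 1 assessment already meets the every-cycle rule there.

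**Conclusion.** The concern holds for MF patients judged stable after cycle 6. It does not extend to AMKL patients, or to MF patients not judged stable, who keep an AE assessment on Day 1 of every cycle. For the affected group, the scheduled AE assessment falls in one cycle of two. Non-serious, non-laboratory events from the clinic-started course are first asked about after 36 to 42 days (mean 39) instead of 15 to 21 (mean 18), and after a second 7-day course.

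The consequence is delayed recall, weaker onset timing for Section 10.1.1, and possible dosing over an unresolved toxicity. The documents do not show how many events would be missed or misdated, nor how many patients will reach this stage, so the effect on AE percentages cannot be sized.

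The figures assume nominal 21-day cycles, onset on a dosing day, no unscheduled report by the patient, and sites doing only what Section 4.2 and footnote m specify. This is a worthwhile, cheap improvement; the primary endpoint remains analysable without it.

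**What to change.** In Section 4.2 and footnote m of Section 5.1, add that before each home-started cycle the coordinator asks about new, ongoing or worsened AEs, records onset dates, and asks specifically about sedation and confusion. The treating physician then reviews the answers together with the CBC and CMP, applying Section 4.3.2, before the cycle is released.

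Sequence matters, because the contact as written delivers the decision. Either the enquiry precedes the physician's review, or any new or unresolved event goes back to the physician before dosing starts.

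The cost is a sentence in each of two places, a few minutes per contact, some data entry and an occasional call-back. Recorded rates of low-grade events may rise slightly because they are asked about more often. No extra clinic visit is needed, so the convenience of the 6-weekly schedule is kept.
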